Before treatment, there will be a 4 week observation-only period, and another one 8 weeks post-treatment, so that the total study period will be 6 months.

We aim for 20 patients to be included in this study.

see more detailed graphics in the next section

In terms of ancillary, laboratory-based studies, we intend to draw blood before treatment and at the 45-, 75-, 105- and 135-day of treatment time-points. We will measure cytokine/chemokine/lipid pain- and inflammation markers in patients' serum, also determine microRNA in their serum, and genomic DNA polymorphisms, the latter only at baseline. Please see next section for more detail.

To establish safety of the anti-CGRP treatment in this patient cohort, blood draw at baseline and at the 45-, 75-, 105- and 135-days of treatment time-points will also include routine systemic sentinel/surveillance markers, namely comprehensive metabolic panel and complete blood count with differential, and complete urinalysis. No more than 45 ml of blood will be collected at any given visit.

In terms of additional safety parameters, we propose an open, patient-kept side-effect log, plus home-based recordings of blood pressure, heart rate and weight at a frequency of 2x/week.

We will set up a data and safety monitoring board for proper management and oversight of data handling and patient safety-related issue; see next section.

[figure not shown]
We expect to observe effective treatment, at least in a significant subgroup of patients. Effectiveness of treatment, also magnitude of any observed therapeutic effect will be correlated with the pain/inflammation proteinaceous, lipid and RNA-based biomarkers in patients' serum, also with any polymorphisms in the patients' genomic DNA.

We also expect galcanezumab treatment to show another record of safe treatment, our expectation sculpted by analysis of in-depth data from treatment of migraineurs. Yet we will remain vigilant and implement the proposed safety sentinel measures in order not to miss adverse effects. This appears prudent because trigeminal or glossopharyngeal nerve pain plus small-fiber neuropathy is a different underlying disorder than migraine, likely representing a higher prevalence in peri-menopausal female patients. We also believe it is likely that level of chronic pain suffering-associated stress will be higher in our study population than in migraineurs.

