In addition, we propose to detect systemic circulatory microRNAs. These molecules will be identified by RNA-seq starting with small RNA-preparation from patients' serum. This approach is preferred over a candidate approach since it is maximally unbiased. We believe that an unbiased approach will be more suitable because pain-associated circulatory miRNA markers are not firmly established, therefore a "candidate approach" is not even feasible. With an open, unbiased discovery approach of miRNAseq we minimize the risk to miss anything of relevance. The number of miRNAs is considered currently slightly >2000, thus very roughly 1/10 of the number of all protein-coding genes. MicroRNAs have been established robustly as biomarkers in specific malignancies, also with chronic inflammation, so that a tentative association with specific pain conditions appears an appealing opportunity to make these discoveries in our patient population.

Baseline blood draw (and only at that time point because it will not change through treatment) will also include preparation of genomic DNA from white blood cells to sequence the patients' genomic DNA whole-exome. Having these data available will position us favorably so that we can identify any genetic abnormalities (e.g. in pain-associated voltage-gated sodium channels, pain-TRP channels, inflammation-associated genes) in our patients. First we will be analyzing the genomic DNA profile for presence of pain susceptibility genes in known genes and their respective families, such as voltage-gated sodium channels, neurogenic inflammation pathway, opioid receptor signaling, MRGPR-X related pathway, pain-TRPs and associated proteins, β -adrenergic signaling, COMT pathways, algogenic lipid mediator pathways, and more. After identification of particular high-responders and low/non-responders, we will try to identify association of these particular response patterns with any measured biomarker, including DNA polymorphisms, miRNA, lipid, protein/peptide markers.

3) Data Safety Monitoring Board (DSMB)

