Patients will be recruited via the PI's clinics at Duke University, the Duke Clinics that typically refer to her attention and outside clinics and providers that refer to her as well, and DEDUCE database. In case of slow recruitment patient self-help and patient advocacy associations in the facial pain arena will be informed of the ongoing study to assist with recruitment. These organizations (Facial Pain Research Foundations, Facial Pain Association) are well-known to the PI.

11) Brief Statistical Analysis Plan

Only patients who complete the study will be included in the statistical analysis.

Response to treatment will be assessed by comparing pain metrics during the 90-day treatment period vs averaged 30 day "run-in". Outcome variables will consist of selected readout parameters of "pain metrics", namely pain subjective rating on VAS (0-10) and medication co-use. Additional outcome variables include circadian rhythm-associated metrics. A daily readout for each variable will be entered into their log by each patient, or by automatic activity reads from their motion tracking device. In similar manner, we will compare pain metrics during the 90-day treatment period vs 60-day post-treatment observation.

We intend to conduct the study with an n=20 patients to successfully complete the study. This selected number appears the most feasible and practicable number. We are confident that with an n=20 we will be in a position to do justice to the objective of initial assessment of the safety of galcanezumab in the condition under study, trigeminal or glossopharyngeal pain in the context of painful small fiber neuropathy/fibromyalgia.

Following completion of the study, we will have estimates of effect sizes and corresponding 95% confidence intervals providing information on the precision of the statistical estimates of treatment effect. Power analysis will be performed based on these estimates and will provide us with guidance for sample sizes of follow-up studies that aim for demonstrating effectiveness.

The statistical analysis will be based on a linear mixed model for repeated measures. The

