time course of pain metrics reported during the treatment period will be compared with metrics during the run-in baseline. The covariance matrix describing the nature of correlations between repeated measures will be selected based on Akaike information criterion and Bayesian information criterion, as guided by our statistics software, SAS/STAT15.1. p-values <0.05 will be considered statistically significant. Effects of treatments will be investigated with the introduction of treatment as a binary covariate (we will evaluate the effects of pre- and post-treatment in two different models).

Patients' anti-pain treatment response will be correlated with blood markers for pain, inflammation and miRNA, and also for genomic markers. This approach will be pursued in order to identify candidate biomarkers that pre-dispose patients to experience an effective or non-effective treatment response. In case of recording any particular safety-related parameters, correlation of these markers to safety metrics will also be conducted. Association between molecular biomarkers and pain- and activity-related metrics will be evaluated (i) at each time point separately using a linear regression model; (ii) by modeling the association across all time points and including time covariate in the linear regression model. The ensemble of these approaches will help determine the periods when pain or activity-related metrics and molecular markers co-evolve and become highly correlated.

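### Biomarker analysis (ii) is written as a linear regression over up to five samples per patient with no patient term, and no multiplicity control is stated for about 2,000 markers

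*Combined protocol and SAP*

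**What the plan says.** The Study Design / Overview section states the intention to "draw blood before treatment and at the 45-, 75-, 105- and 135-day of treatment time-points". Section 2 (Blood draw: detailed analysis) repeats this schedule, which gives up to five serum samples per patient. It lists 39 serum cytokines, chemokines, lipid mediators and peptides. It adds an open miRNA sequencing screen, with the remark "The number of miRNAs is considered currently slightly >2000". Exome variants are taken once, at baseline.

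Section 11 plans for 20 completers. Its model statement is general: "The statistical analysis will be based on a linear mixed model for repeated measures". The next sentence applies it to pain, where the "time course of pain metrics reported during the treatment period will be compared with metrics during the run-in baseline". Within-patient correlation is addressed there: "The covariance matrix describing the nature of correlations between repeated measures will be selected based on Akaike information criterion" and the Bayesian criterion. The same paragraph holds the only decision rule, "p-values <0.05 will be considered statistically significant".

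The biomarker paragraph that follows names a different model. Analysis (i) works "at each time point separately using a linear regression model". Analysis (ii) proceeds "by modeling the association across all time points and including time covariate in the linear regression model". For (ii) the paragraph names no patient effect, covariance structure or clustered standard error. No multiplicity rule appears anywhere in the documents.

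**The concern.** Ordinary linear regression assumes independent rows. Analysis (i) meets this, with one row per patient at each time point. Analysis (ii) stacks the time points, so each patient contributes up to five rows. A time covariate removes a shared trend over time. It does not remove the tendency of one patient's values to resemble each other. If both marker and outcome carry such a tendency, the standard error is too small and so are the p-values.

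The second gap is the size of the search. With 39 serum markers, about 2,000 miRNAs and exome variants, and no statement on multiplicity, a reader cannot tell how many reported associations chance alone would produce.

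The biomarker work is a secondary, exploratory aim. Its purpose is to supply candidates for later studies, so what is at stake is the quality of that candidate list.

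**Working it through.** The plan gives no error rate or power for the biomarker analyses, so there is no figure to reproduce.

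**Inputs from the documents.** 20 completers (section 11); five draws, pre-treatment and days 45, 75, 105 and 135 (Overview and section 2); 39 serum markers and about 2,000 miRNAs (section 2); significance at 0.05 (section 11).

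**Assumptions.** Two-sided tests; day 0 for the pre-treatment draw; the within-patient correlation (ICC) of marker and outcome, which the documents do not give.

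**1. Type I error of (ii) as written.** With constant within-patient correlation and no true association, the variance of the slope is understated by about

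D = 1 + (5 − 1) × ICC(marker) × ICC(outcome),

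and the true error rate is about 2 × [1 − Φ(1.96/√D)]. Example at 0.5 and 0.5: D = 1 + 4 × 0.25 = 2.00; 1.96/√2.00 = 1.386; error rate 0.166.

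The formula was checked by null simulation of outcome on marker plus time, 20 patients × 5 draws, 200,000 data sets per setting. A decaying pattern was also simulated, with the tabulated value as the correlation per 30 days.

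| Correlation (marker = outcome) | D | Formula | Simulated, constant | Simulated, decaying |
|---|---|---|---|---|
| 0 | 1.00 | 0.050 | 0.050 | – |
| 0.2 | 1.16 | 0.069 | 0.068 | 0.056 |
| 0.3 | 1.36 | 0.093 | 0.091 | 0.064 |
| 0.5 | 2.00 | 0.166 | 0.166 | 0.099 |
| 0.7 | 2.96 | 0.255 | 0.261 | 0.176 |
| 0.8 | 3.56 | 0.299 | 0.309 | 0.236 |

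With one ICC at 0 and the other at 0.7, the simulated rate is 0.049 to 0.050, so there is no inflation.

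A baseline DNA variant entered in (ii) would be constant within patient (ICC 1). At outcome ICC 0.3, 0.5 and 0.7, D = 2.2, 3.0 and 3.8, and the formula gives 0.19, 0.26 and 0.31.

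**2. Chance hits if p<0.05 is applied to each marker, per outcome.** For a valid test: 39 × 0.05 = 1.95 serum markers and 2,000 × 0.05 = 100 miRNAs. If every marker and the outcome had a constant ICC of 0.5: 39 × 0.166 = 6.5 and 2,000 × 0.166 = 332. At 0.8: 39 × 0.309 = 12 and 2,000 × 0.309 = 618.

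**3. Does a mixed model repair (ii)?** REML fits, 3,000 null data sets each, at correlations 0.3, 0.5, 0.7 and 0.8, t test on 78 df:

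| Model for (ii) | Constant-correlation data | Decaying data |
|---|---|---|
| Random patient intercept only | 0.055, 0.055, 0.045, 0.054 | 0.055, 0.079, 0.092, 0.100 |
| Better-fitting of random intercept and time-decay covariance | 0.057, 0.058, 0.045, 0.055 | 0.048, 0.057, 0.053, 0.060 |

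The two structures have the same number of parameters, so AIC and BIC make the same choice. The covariance selection step is needed: a random intercept alone still reaches 10% under decay.

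**4. What a false discovery rate rule would demand.** For a lone marker to pass at 5%, its p-value must be at most 0.05/m for m tests. The required correlation is |r| = t/√(t² + df), where t is the two-sided critical value at 0.05/m. With one row per patient and one adjusting covariate, df = 20 − 3 = 17. The larger test counts assume 5 time points and 3 outcomes.

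| Tests, m | t, df 17 | Required r (absolute), df 17 | Required r (absolute), df 18 (no covariate) |
|---|---|---|---|
| 39 | 3.851 | 3.851/√(14.83 + 17) = 0.683 | 0.668 |
| 39 × 5 × 3 = 585 | 5.119 | 0.779 | 0.765 |
| 2,000 × 5 × 3 = 30,000 | 7.136 | 0.866 | 0.854 |

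**The case against.** **The mixed model may be meant to cover (ii).** The sentence introducing it is unrestricted, the section is headed as brief, and the authors plainly know that repeated measures correlate. A mixed model is also a kind of linear regression. This could be the intention, but it is not what is written. The sentences after that statement concern pain metrics, and the biomarker paragraph uses the same term for (i), where ordinary regression is right, and for (ii), where the only stated addition is time.

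**The correlations are assumed, and equal values are unfavourable.** This is fair. For a given average the product of the two ICCs is largest when they are equal, and marker correlations will not all match the outcome's. The formula gives 12.6% at 0.2 and 0.8, 9.3% at 0.1 and 0.9, 9.8% at 0.2 and 0.5, and 7.4% at 0.1 and 0.5. These are smaller than the equal-correlation figures for the same averages, but all exceed 5%.

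**Formal multiplicity control is not obligatory in an open-label pilot of 20 patients seeking candidates.** This stands. The biomarker paragraph states no decision rule, so the chance-hit counts rest on carrying over p<0.05 from the pain paragraph. What remains is that nothing labels these p-values as unadjusted or descriptive.

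**The check of the remedy used time-varying markers.** For a marker measured once, such as a DNA variant, the information lies between patients, with about 18 df. Using the 78-df cut-off would give about 6.2%. This is a minor point about degrees of freedom.

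**Conclusion.** The concern holds. As written, (ii) is the wrong model for repeated samples, and the plan's own remedy for within-patient correlation is not extended to it. The true error rate of a nominal 5% test is about 7% to 31% for equal constant correlations of 0.2 to 0.8, and about 6% to 24% if correlation decays at those values per 30 days. It is lower for unequal correlations and 5% if either is zero. These sizes rest on assumed correlations; the direction does not, provided both marker and outcome are positively correlated within patient.

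The missing multiplicity statement is a separate gap. It matters for how candidates are read, not for any confirmatory claim. Safety and pain conclusions do not depend on either point. The plan should be changed, but the trial's main objectives are not at risk.

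**What to change.** - State that (ii) uses the linear mixed model for repeated measures already planned for pain metrics. Include a patient term, for example a random intercept, and choose the covariance structure by the AIC/BIC rule already in section 11. Analysis (i) can stay as it is.
- For markers measured once, use between-patient degrees of freedom.
- Report Benjamini-Hochberg q-values beside ranked raw p-values, within separate serum, miRNA and DNA-variant families. Define each family's test count over the time points and outcomes tested.
- Label all biomarker results exploratory.

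The cost is a few sentences in the SAP and a few lines of code, with no extra samples. The downside is that with 20 patients few or no markers may pass: a lone marker needs |r| of about 0.68 for 39 tests and about 0.87 for 30,000. This is why the ranked raw p-values should stay in the report.

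### The pooled marker–pain regression names a time covariate but no treatment-phase or patient term; if time is linear, shifts shared across the off–on–off schedule can pass for a marker–pain link.

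*Combined protocol and SAP*

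**What the plan says.** Section 11 (Brief Statistical Analysis Plan) gives two analyses of molecular markers against pain and activity metrics. The first is a regression "at each time point separately using a linear regression model". The second pools the draws "by modeling the association across all time points and including time covariate in the linear regression model". The form of time is not stated, and no phase or patient term is named for the pooled model. The stated purpose is that the approaches together "will help determine the periods when pain or activity-related metrics and molecular markers co-evolve and become highly correlated".

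The same section does have a treatment term, "Effects of treatments will be investigated with the introduction of treatment as a binary covariate", but it describes the mixed model for pain metrics and not the marker regression. The threshold, "p-values <0.05 will be considered statistically significant", stands in that same paragraph. I assume that it also applies to the marker models and is two-sided.

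The Study Design / Overview describes one open-label arm: four weeks of observation, 12 weeks of treatment and eight weeks of further observation. It plans to "draw blood before treatment and at the 45-, 75-, 105- and 135-day of treatment time-points". Section 11 sets the size: "We intend to conduct the study with an n=20 patients to successfully complete the study". That gives up to 20 × 5 = 100 marker–pain pairs.

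**The concern.** The protocol expects pain to fall on treatment and lists improvement in serum inflammation markers as an objective. CGRP, which the drug neutralizes, is on the marker panel. Both sides of the regression may therefore move with treatment phase and move back afterwards, in every patient at the same draws. A straight line in time cannot follow a fall and a return. What it leaves behind is common to marker and pain, and it loads onto the marker coefficient.

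A patient term alone does not remove this, because the pattern is the same in all patients. At stake is what a positive result means: it could show a marker that tracks a patient's pain, or only one that responds to the drug over the period in which pain also changed. Separately, an ordinary regression on up to five draws per patient treats correlated values as independent.

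**Working it through.** The plan gives no figure for this model, so there is nothing to reproduce. The shifts and SDs below are assumptions.

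**1. How much of the on/off pattern a straight line absorbs.** Take days 0, 45, 75, 105 and 135, with mean 72 and Sxx = 72² + 27² + 3² + 33² + 63² = 10,980. For an on/off indicator z, R² = Sxz² / (Sxx × Szz).
- Off, on, on, on, off (draw days counted as study days): Sxz = −27 + 3 + 33 = 9 and Szz = 1.2, so R² = 81/13,176 = 0.6%.
- Off, on, on, off, off (counted as days since first dose): Sxz = −27 + 3 = −24 and Szz = 1.2, so R² = 576/13,176 = 4.4%.
- Off, then on at every later draw (effect persists): Sxz = 72 and Szz = 0.8, so R² = 5,184/8,784 = 59%.

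A five-level visit factor absorbs 100% in each case.

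**2. Effect on the marker coefficient, linear time plus patient intercepts.** Use the first pattern, equal shifts s in marker and pain, visit SD 0.6 and no true link. The shared sum of squares left after linear time is 20 × 1.2 × (1 − 0.006) = 23.85 per unit s². The noise sum of squares is 0.36 × (100 − 21) = 28.44.
- s = 0.5: r = 5.96/(5.96 + 28.44) = 0.173; t ≈ 0.173 × √(78/0.970) = 1.55. Against a critical value of 1.99 this rejects about 33% of the time.
- s = 1.0: r = 23.85/(23.85 + 28.44) = 0.456; t ≈ 0.456 × √(78/0.792) = 4.5, which rejects about 99% of the time.

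**3. Ignoring the repeated draws, no shift at all.** With patient SD 0.8 and visit SD 0.6, the intraclass correlation is 0.64/(0.64 + 0.36) = 0.64. The variance of the slope is understated by a factor of about 1 + 4 × 0.64² = 2.64. The effective critical value is 1.985/√2.64 = 1.22, so the false-positive rate is about 22%. At a correlation of 0.5 the factor is 2 and the rate about 16%.

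**4. Simulation.** 5,000 runs, 20 patients, five draws, marker and pain generated independently apart from the shared pattern, fixed patient intercepts where a patient term is used, two-sided 0.05.

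| Shared pattern | Shift | Linear time, no patient term | Linear time + patient | Visit factor, no patient term | Visit factor + patient |
|---|---|---|---|---|---|
| none | 0 | 21% | 5% | 21% | 5% |
| 0, 1, 1, 0.5, 0 | 0.5 | 23% | 25% | 23% | 5% |
| 0, 1, 1, 0.5, 0 | 1.0 | 44% | 99% | 24% | 5% |
| 0, 1, 1, 1, 0 | 0.5 | 24% | 34% | 23% | 5% |
| 0, 1, 1, 1, 0 | 1.0 | 52% | >99% | 23% | 5% |
| 0, 1, 1, 0, 0 | 0.5 | 23% | 32% | 23% | 5% |
| 0, 1, 1, 0, 0 | 1.0 | 51% | >99% | 23% | 5% |
| 0, 1, 1, 1, 1 | 0.5 | 23% | 8% | 23% | 5% |
| 0, 1, 1, 1, 1 | 1.0 | 24% | 40% | 23% | 5% |
| 0, 0.5, 1, 1, 1 | 0.5 | 23% | 6% | 23% | 5% |
| 0, 0.5, 1, 1, 1 | 1.0 | 23% | 12% | 23% | 5% |

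Repeat sets of runs moved entries by up to about two percentage points. At a shift of 0.25 in the reversing patterns, linear time plus patient gives about 7%. If the marker shifts by 1.0 and pain does not shift, the patient-effect model gives about 5%. A random patient intercept in place of fixed ones (2,000 runs) gives 24 to 29% and 96 to 99% for linear time in the reversing patterns, and 5 to 6% for the visit factor.

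**The case against.** **The plan does not say that time is linear.** This stands. A covariate for time is most naturally read as a continuous term, but with five discrete draws a visit factor is compatible with the text. It would remove the shared shift completely.

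**The largest rates belong to a model that the plan does not contain.** This stands too. The 98% and above needs a patient effect, which the marker regression does not name. In the model as written, most of the excess at small and moderate shifts comes from ignoring repeated draws, and a visit factor alone leaves about 23%.

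**The result depends on reversal.** The documents give no washout figure. They also label days 105 and 135 as days of treatment, although treatment lasts 12 weeks or 90 days. If the shifts persist, the rates are much lower.

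**The analysis is exploratory, and co-movement is partly its aim.** Fair: these are ancillary candidate biomarkers in a pilot whose first criterion is safety. The regression at each time point is untouched by a shift common to all patients. But co-movement across phases does not by itself show that a marker is tied to a patient's pain, and the plan also looks for association and for candidate markers of response.

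A reader might infer that any marker moved by the drug will appear pain-related. The documents do not support that: pain must shift over the same phases as well, and both shifts must be large relative to visit-to-visit noise.

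**Conclusion.** The point holds in limited form. The pooled marker model leaves the form of time open and names neither a phase nor a patient term, in a design where all patients share one off–on–off schedule. Under the linear reading, shared shifts that reverse produce false associations. With a patient effect the rate is about 25 to 34% at a shift of 0.5 (0.83 visit SDs) and at least 98% at 1.0 (1.67 visit SDs). If the shifts persist, it is about 6 to 40%. As written, without a patient term, the reversing patterns give about 23% and 44 to 52%, against a floor above 20% with no shift at an assumed intraclass correlation of 0.64. All these figures rest on assumed shifts, SDs and time patterns. It would go too far to say that the plan's time term cannot follow the design, since that is true only if the term is linear. The regressions by time point and the pain-metric mixed model are not affected. The change is worth making because it is cheap and settles what a positive pooled result means.

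**What to change.** In the pooled marker analysis of section 11, make two changes together:
- Enter time as a five-level visit factor (the pre-treatment draw and the four later draws).
- Add a patient effect, using a mixed model as the section already does for pain metrics.

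Report any co-movement across visits that is not adjusted for visit as descriptive only.

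Separately, reconcile the labelling of days 105 and 135 with the stated treatment period, because it decides which draws count as on treatment. The visit factor works under either reading.

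The cost is a short text change with no new data or visits: three extra degrees of freedom (four for visit in place of one for linear time) plus the patient term. The adjusted coefficient no longer uses the average movement across visits, so that movement has to be described separately.

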We also expect that the proposed studies will be very important for guiding future, more in-depth studies involving larger patient cohorts, placebo-controlled/double-blinded studies, which will possibly lead us toward a personalized-medicine approach.

Study Design Detail

1) Schedule of Activities over Time

2) Blood draw: detailed analysis

Before treatment, and at 45th, 75th, 105th and 135th day of treatment, we propose to assess the following blood parameters, related to pain-associated biomarkers in the systemic circulation.

For this, we propose to study cytokine/chemokine pain- and inflammation markers in patients' serum, using commercially available protein multiplex detection assays. In serum, the following 39 cytokines/chemokines/lipid mediators/peptides will be measured: EPO, GM-CSF, IFN- γ , IL-1 β , IL-2, IL-4, IL-5, IL-6, IL-9, IL-10, IL-12/IL-23p40, IL-12p70, IL-13, IL-15, IL-16, IL-17A, IL-17A/F, IL-17C, IL-17E/IL-25, IL-17F, IL-21, IL-22, IL-23, IL-27p28/IL-30, IL-31, IL-33, IP-10, KC/GRO, MCP-1, MIP-1 α , MIP-1 β , MIP-2, MIP-3 α , TNF- α , VEGF-A, TGF- β , CGRP, Resolvin-D1, Prostaglandin-E2. For these measurements, we will be using a human 35-plex ELISA (U-PLEX Biomarkers) and single ELISAs (Signosis; Cayman).

These are key mediators and indicators of pain and inflammation. We believe it will be feasible to conduct these assays. For each marker there is sufficient evidence supporting its role in pro-algesic inflammation or organismal response to tissue damage. We are

convinced that their ensemble will prove a powerful source of mechanistic data that will elucidate treatment responses to galcanezumab in our patient population.

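### Neither planned marker regression can show that pain and markers co-evolve within patients, or date the periods when they do

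*Combined protocol and SAP*

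**What the plan says.** The last paragraph of section 11 relates molecular markers to pain and activity metrics in two ways. Analysis (i) is run "i) at each time point separately using a linear regression model". Analysis (ii) is a single linear regression over all time points with time as a covariate. The plan then concludes that the two together "will help determine the periods when pain or activity-related metrics and molecular markers co-evolve and become highly correlated".

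The data behind this are set elsewhere. Section 2 (Blood draw) gives five draws: "Before treatment, and at 45th, 75th, 105th and 135th day of treatment, we propose to assess the following blood parameters". Section 11 gives the sample: "We intend to conduct the study with an n=20 patients to successfully complete the study", and "Only patients who complete the study will be included in the statistical analysis".

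For the marker analysis the plan states no marker-by-time term, no test of a difference between draws, no patient effect, no within-patient term, and no criterion for a period or for a high correlation. The linear mixed model in section 11 is described for the time course of pain metrics against run-in, not for the marker associations.

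**The concern.** Co-evolution is a statement about one patient over time: when the marker rises or falls, pain moves with it. A regression at a single draw compares different patients. It can be strongly positive because patients with more pain always have a higher marker, even if the two never move together in anyone.

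Dating a period requires a further step, namely evidence that the association differs between draws. Five separate fits side by side do not provide it: a clear association at one draw and a weak one at the next is what sampling error produces at n=20. Analysis (ii) could have filled the gap, but as written it returns one average slope.

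At stake is that stable patient differences plus noise are described as time-specific biology, in a study whose Overview says it should guide larger ones.

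**Working it through.** The plan gives no error rate or power for this analysis, so there is no figure to reproduce.

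**Inputs from the documents.** n = 20 completers; five draws; threshold 0.05 ("p-values <0.05 will be considered statistically significant", stated in the paragraph on the treatment model; its use for the marker regressions, and two-sided, is my assumption).

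**Assumptions not in the documents.** Marker and pain each consist of a stable patient level plus independent visit-to-visit variation. The ICC (share of variance that is stable) runs from 0.3 to 0.9. The patient levels correlate at ρ. Visit-to-visit variation in marker and pain is independent, so nothing co-evolves and the true correlation is ρ × ICC at every draw.

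**Step 1: precision at one draw.** Significance needs |r| ≥ t/√(18 + t²), with t = 2.101 on 18 df: 2.101/√22.41 = 0.444. At r = 0.444, Fisher z = 0.477 with SE 1/√17 = 0.243, so the 95% CI is 0.477 ± 0.475 on the z scale, or 0.00 to 0.74 for r. In simulation with a constant true r of 0.35 to 0.49 (ICC 0.5 to 0.7), the sample r of one marker differs by about 0.3 to 0.4 between its highest and lowest draw by chance alone.

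**Step 2: false periods from (i).** As a working definition, count a pair as showing a period if p<0.05 at some but not all five draws. With no relation and independent draws, the chance of at least one significant draw is 1 − 0.95⁵ = 0.226. Simulated rates for one marker-metric pair:

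| Between-patient ρ | ICC 0.3 | ICC 0.5 | ICC 0.7 | ICC 0.9 |
|---|---|---|---|---|
| 0 (no relation) | 22% | 21% | 20% | 13% |
| 0.5 | 37% | 58% | 64% | 45% |
| 0.7 | 51% | 77% | 70% | 25% |
| 0.9 | 66% | 83% | 35% | 1% |

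Repeat runs moved entries by about 2 points at most, hence the quoted ranges: 12% to 23% for ρ = 0, and 24% to 77% for ρ of 0.5 to 0.7 at ICC 0.5 to 0.9. The rate falls to about 1% when the constant correlation is very strong (true r = 0.9 × 0.9 = 0.81), because all five draws are then significant.

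**Step 3: does (ii) repair this?** With only a time covariate it has one slope, so it cannot say when anything happened. It also treats 20 × 5 = 100 readings as independent. With no relation, the variance of the pooled slope is understated by about 1 + 4 × ICC², so the true rejection rate is about 2 × P(Z > 1.96/√(1 + 4 × ICC²)):

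| ICC | 1 + 4 × ICC² | 1.96/√ | Formula | Simulation |
|---|---|---|---|---|
| 0.3 | 1.36 | 1.68 | 9% | 9% |
| 0.5 | 2.00 | 1.39 | 17% | 16% |
| 0.7 | 2.96 | 1.14 | 25% | 25% |
| 0.9 | 4.24 | 0.95 | 34% | 35% |

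With a between-patient relation only (ρ = 0.5, ICC 0.3 to 0.9), (ii) rejects 33% to 91% of the time although nothing co-evolves.

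**Step 4: the alternative.** A slope on each patient's deviations from their own mean, adjusted for draw, rejects in 4% to 6% of simulations in every setting above. With a true within-patient correlation of 0.5 it detects the association in more than 99% of data sets; a regression at a single draw does so in 10% (ICC 0.7) to 18% (ICC 0.5).

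**The case against.** The plan does not rely on separate fits alone. It names an all-draws model as well and says only that the two will help determine periods. That is fair, and a reader who infers that the longitudinal data are ignored would be wrong. But (ii) as written lacks the two terms that the claim needs. If a marker-by-time term or patient effects were intended, the text does not say so.

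A reader might also infer that the plan defines a period as significance at some draws and not others. It does not: it speaks of high correlation and gives no rule, and the 0.05 threshold stands in the paragraph on the treatment model. The rates in Step 2 therefore show what follows from one natural reading, not from a stated rule.

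Nor do the documents support saying that periods will always be reported. With no relation, most single pairs show none. Over the whole panel ("the following 39 cytokines/chemokines/lipid mediators/peptides will be measured", plus miRNAs) some would be likely, but that is mainly a multiplicity matter, separate from the inference examined here.

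Finally, this is a 20-patient open-label pilot in search of candidate biomarkers. That limits the consequence and stands in full. It does not make the inference valid.

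**Conclusion.** The concern holds as a mismatch between a stated conclusion and the analyses named for it. Analysis (i) measures between-patient association with no comparison across draws. Analysis (ii) cannot date a period, mixes between-patient with within-patient association, and over-rejects at about 9% to 35% with no relation at all.

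The size of the false-period problem depends on an assumed rule and on ICCs and correlations that the documents do not give: about 12% to 23% per pair with no relation, about 24% to 77% with a constant between-patient correlation of 0.5 to 0.7, and near 1% when that correlation is very strong. No single value should be quoted.

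It would go too far to infer that the safety or primary pain results are affected: those analyses do not use the marker regressions. The point should be corrected, but it concerns exploratory biomarker conclusions only.

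**What to change.** Replace (ii) with one repeated-measures model over all draws, with a patient effect and draw as a factor. Enter each marker as two terms: the patient's mean and the deviation from it at each draw. An equivalent within-patient method would also serve.

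Then tie the wording to the terms:

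- Speak of co-evolution only for the within-patient (deviation) slope, reported with its 95% CI.
- Name a period only if a deviation-by-draw interaction supports it.
- Keep the per-draw regressions in (i) as descriptive displays.

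The cost is a few sentences of SAP text and one model on data already planned; no extra visits or samples are needed. The drawback is that the interaction test has low power at n=20, so fewer periods will be claimed. The power above 99% in Step 4 belongs to the overall within-patient slope, not to this interaction.
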